**Appendix 5. Disease Response Assessment by Modified IMWG Criteria**

IMWG Response Criteria	
CATEGORY	RESPONSE CRITERIAa
Stringent Complete Response (sCR)	
CR as defined below plus all of the following:
 
 
• Normal serum FLC ratio
 
• Absence of clonal cells in bone marrow by immunohistochemistry or immunofluorescenceb
 

Complete Response (CR)	
 
• Negative immunofixation of the serum and urine
 
• <5% plasma cells in bone marrow
 
• Disappearance of any soft tissue plasmacytomas
 
• If at on study, the only measurable non-bone marrow parameter was FLC, normalization of FLC ratio
 

Very Good Partial Response (VGPR)c	
 
• PR as defined below plus all of the following:
 
• Serum and urine M-component detectable by immunofixation but not on electrophoresis or
 
• If at on study, serum measurable, <math>\geq 90\%</math> or greater reduction in serum M-component plus urine M-component <100 mg per 24 h
 
• If at on study, the only measurable non-bone marrow parameter was FLC, <math>\geq 90\%</math> or greater reduction in the difference between involved and uninvolved free light chain levels
 

Partial Response (PR)	
 
• One of the following: 
 
▪ If at on study, serum and urine measurable, a <math>\geq 50\%</math> reduction of serum M-protein and reduction in 24-h urinary M-protein by <math>\geq 90\%</math> or to <200 mg per 24 h
 
▪ If at on study, only serum measurable (but urine not), a <math>\geq 50\%</math> reduction of serum M-protein
 
▪ If at on study, urine measurable (but serum not), a reduction in 24-h urinary M-protein by <math>\geq 90\%</math> or to <200 mg per 24 h
 
▪ If at on study, the only measurable non-bone marrow parameter was FLC, a <math>\geq 50\%</math> decrease in the difference between involved and uninvolved FLC levels
 
▪ If at on study, the bone marrow was only measurable parameter, <math>\geq 50\%</math> reduction in bone marrow plasma cells is required in place of M-protein, provided baseline percentage was <math>\geq 30\%</math>
 
 
 
• In addition to the above criteria, if a plasmacytoma present at baseline, <math>\geq 50\%</math> reduction in the size of soft tissue plasmacytomas is also required
 

Minimal Response (MR)	
 
• <math>\geq 25\%</math> but <math>\leq 49\%</math> reduction of serum M-protein and reduction in 24h urine M-protein by 50-89%,
 
• In addition to the above criteria, if a plasmacytoma present at baseline, 25-49% reduction in the size of soft tissue plasmacytomas is also required
 
• No increase in size or number of lytic bone lesions (development of compression fracture does not exclude response)
 

Stable Disease (SD)	Not meeting criteria for CR, VGPR, PR, MR or progressive disease

IMWG Response Criteria	
CATEGORY	RESPONSE CRITERIA a
Progressive Disease (PD)	
Any one or more of the following:
 
 
• Increase of 25% from lowest value in g: 
 
▪ Serum M-component (absolute increase must be <math>\geq 0.5</math> g/dL)c
 
▪ Serum M-component increase <math>\geq 1</math> g/dL, if starting M component was <math>\geq 5</math> g/dL
 
▪ Urine M-component (absolute increase must be <math>\geq 200</math> mg/24 h)c
 
▪ If at on study, the only measurable non-bone marrow parameter was FLC, the difference between involved and uninvolved FLC levels (absolute increase must be <math>>10</math> mg/dL)c
 
▪ Bone marrow plasma cell percentage (absolute % must be <math>\geq 10\%</math>)c
 
 
 
 
Or any one or more of the following felt related to the underlying clonal plasma cell proliferative disorder
 
 
▪ Development of new soft tissue plasmacytomas or bone lesions
 
▪ Hypercalcemia (<math>\geq 11.5</math> mg/dL)
 

Relapse from CR or sCR d	
Subject who has achieved confirmed CR who has any one or more of the following:
 
 
• Reappearance of serum or urine M-protein by immunofixation or electrophoresis
 
• Development of <math>\geq 5\%</math> plasma cells in the bone marrow f
 
• Appearance of any other sign of progression (i.e., new plasmacytoma, lytic bone lesion, or hypercalcemia)
 

a All response categories require two consecutive assessments made at any time before the institution of any new therapy; complete response and PR, MR and SD categories also require no known evidence of progressive or new bone lesions if radiographic studies were performed. Radiographic studies are not required to satisfy these response requirements. Bone marrow assessments need not be confirmed.

b Presence/absence of clonal cells is based upon the k/ $\lambda$  ratio. An abnormal k/ $\lambda$  ratio by immunohistochemistry and/or immunofluorescence requires a minimum of 100 plasma cells for analysis. An abnormal ratio reflecting presence of an abnormal clone is k/ $\lambda$  of  $>4:1$  or  $<1:2$ .

c Positive immunofixation alone in a subject previously classified as CR will not be considered progression.

d This category will ONLY be used to analyze disease free survival

e This response category is not available for those subjects being followed by bone marrow only.

f Relapse from CR has the 5% cutoff versus 10% for other categories of relapse.

g In the case where a value is felt to be a spurious result per physician discretion (for example, a possible lab error), that value will not be considered when determining the lowest value.

### Confirmation of Response Categories

In order to be classified as a hematologic response, confirmation of serum monoclonal protein, serum immunoglobulin free light chain (when primary determinant of response) and urine monoclonal protein (when primary determinant of response) results must be made by verification on two consecutive determinations. Confirmation assessments may be performed at any time after the initial assessment.

- Bone marrow aspirate/biopsy is **only** required to document CR or sCR, except for subjects with bone marrow plasmacytosis evaluable disease **only**, where a bone marrow is required to document all response categories including progression. However, a second confirmatory bone marrow is not required to confirm response in any case
- Radiographic studies are not required to satisfy these response requirements; however, if radiographic studies were performed there should be no evidence of progressive or new bone lesions.

### Measurable Disease

- Serum M-protein  $\geq 0.5$  g/dL
- Urine M-protein  $\geq 200$  mg/24 h
- Serum FLC assay: Involved FLC level  $\geq 10$  mg/dL provided serum FLC ratio is abnormal

The serum free light chain (sFLC) assay is of particular use in monitoring response to therapy in subjects who have oligo-secretory or non-secretory disease and **should be used in assessing response only if the baseline serum and/or urine M proteins are not “measurable” as above, and the baseline level of the involved FLC is “measurable.”** When using this assay, it is important to note that the sFLC levels vary considerably with changes in renal function and in subjects with renal insufficiency, the levels of both the kappa and lambda may remain elevated, but the ratio normalizes with achievement of CR. Thus, both the level of the involved and the uninvolved sFLC isotype (ie, the involved/uninvolved ratio or involved-uninvolved difference) should be considered in assessing response. ***Subjects included on the study on the basis of sFLC alone (ie, no measurable serum/urine m-spike) should be the only ones who are evaluated using sFLC response criteria. The others should follow usual criteria and ignore sFLC results*** with the exception of defining stringent complete response.

**Appendix 6. Child-Pugh Score for Subjects with Liver Impairment**

Measure	1 point	2 points	3 points
Total bilirubin, $\mu\text{mol/L}$ (mg/dL)	<34 (<2)	34-50 (2-3)	>50 (>3)
Serum albumin, g/L (g/dL)	>35 (>3.5)	28-35 (2.8-3.5)	<28 (<2.8)
PT/INR	<1.7	1.71-2.30	>2.30
Ascites	None	Mild	Moderate to Severe
Hepatic encephalopathy	None	Grade I-II (or suppressed with medication)	Grade III-IV (or refractory)

Points	Class
5-6	A
7-9	B
10-15	C

Source:

8.9.4.	Electrocardiogram	33
8.9.5.	Vital Signs and Physical Examination Findings	33
8.9.6.	ECOG Performance Status	33
9.	PATIENT REPORTED OUTCOME	33
9.1.	NEUROPATHY ASSESSMENT	33
9.2.	BONE PAIN ASSESSMENT.....	34
10.	MODIFICATIONS TO THE PROTOCOL	34
	REFERENCES	36
	APPENDIX 1 PREFERRED TERMS FOR CYP3A4 INHIBITORS/INDUCERS.....	37
	APPENDIX 2 HAEMORRHAGE SEARCH TERMS	38

REVISION HISTORY

Version	Date	Version Description
1.0	05SEP2013	Original version
2.0	15APR2015	SAP was updated to reflect changes in Protocol Amendment 4.
3.0	28OCT2015	SAP was revised to update the definition of progressive disease per modified IMWG for efficacy analysis and to reflect changes in Protocol Amendment 5.
4.0	16JUN2016	SAP was revised to 1) remove detailed definition of study completion as the definition of study completion will be per protocol, and to 2) update preferred terms for CYP3A4 inhibitors in Appendix 1 per newly revised company standard.

ABBREVIATIONS

AE	Adverse event
ALP	Alkaline phosphatase
ALT	Alanine aminotransferase
ANC	Absolute neutrophil count
AST	Aspartate aminotransferase
Btk	Bruton's tyrosine kinase
CBR	Clinical benefit response
CI	Confidence interval
Clcr	Creatinine clearance rate
CR	Complete response or complete remission
CRF	Case report form
CTCAE	Common Terminology Criteria for Adverse Events
CYP	Cytochrome P450
DCB	Duration of benefit
DILI	Drug-Induced Liver Injury
DOR	Duration of response
ECOG	Eastern Cooperative Oncology Group
ECG	Electrocardiogram
FISH	Fluorescent in situ hybridization
Hgb	Hemoglobin
HI	Hematologic improvement
MedDRA	Medical Dictionary for Regulatory Activities
IMiD	Immunomodulatory drug
IMWG	International Myeloma Working Group
IRC	Independent review committee
mITT	Modified intent-to-treat
MM	Multiple myeloma
MR	Minimal response
NCI	National Cancer Institute
ORR	Objective response rate

OS	Overall survival
PD	Progressive disease/disease progression
PFS	Progression-free Survival
PI	Proteasome inhibitors
PK	Pharmacokinetic(s)
PR	Partial response or partial remission
SAE	Serious adverse event
SAP	Statistical analysis plan
SAS	Statistical analysis system
sCR	Stringent complete response
SD	Stable disease
SFLC	Serum free light chain
SPEP	Serum protein eletrophoresis
TCB	Time to clinical benefit
TEAE	Treatment emergent adverse event
TSHI	Time to sustained hematologic improvement
TTP	Time to progression
TTR	Time to response
UPEP	Urine protein eletrophoresis
VGPR	Very good partial response

1. INTRODUCTION

The purpose of this statistical analysis plan (SAP) is to provide a comprehensive description of the final statistical analyses for efficacy and safety data that have been outlined within the protocol.

This plan does not cover the analyses for pharmacokinetic (PK) and biomarker data. The PK analysis will be performed separately and included in the clinical study report. The biomarker data will be analyzed and reported separately from the clinical study report.

The SAP is based on protocol Amendment 5, dated 25 August, 2015. Any changes to the protocol analysis plan, including additional analyses are documented here.

1.1. Protocol Number and Title

Study PCYC-1111-CA: A Multicenter Phase 2 Study of the Bruton's Tyrosine Kinase (Btk) Inhibitor, PCI-32765, in Subjects with Relapsed or Relapsed and Refractory Multiple Myeloma.

1.2. Study Objectives

1.2.1. Primary Objective

The primary objective of this study is to determine the efficacy of ibrutinib (PCI-32765), both as a single agent and in combination with dexamethasone, in subjects with relapsed or relapsed and refractory multiple myeloma (MM) as measured by clinical benefit response (CBR) rate, defined as the proportion of subjects who achieved stringent complete response (sCR), complete response (CR), very good partial response (VGPR), partial response (PR), or minimal response (MR) as assessed by the modified International Myeloma Working Group (IMWG) response criteria^{1,3,6} (see protocol Appendix 6).

1.2.2. Secondary Objectives

Secondary objectives are to evaluate the efficacy, safety and pharmacokinetics of ibrutinib in this population as assessed by the following:

- Duration of clinical benefit (DCB; MR or better)
- Objective response rate (ORR) defined as the proportion of subjects who achieved sCR, CR, VGPR, or PR (ORR; PR or better)
- Duration of objective response (DOR)
- Safety (assessed by reporting of SAEs, AEs, and treatment-related discontinuations)

-
- Pharmacokinetics (assessed by sampling and testing for drug and metabolite levels at designated time points)

1.2.3. Exploratory Objectives

Exploratory objectives are to evaluate the following:

- Progression-free survival (PFS)
- Time to progression (TTP)
- Overall survival (OS)

1.2.4. Exploratory Analyses

- Prognostic and predictive biomarkers and genetics relative to treatment outcomes

1.3. Study Design

This is a Phase 2, open-label, nonrandomized, multi-cohort, multicenter Simon 2-stage study designed to assess the safety and efficacy of ibrutinib in subjects with relapsed or relapsed and refractory multiple myeloma.

Treatment of ibrutinib 420 mg once daily in the original protocol (hereafter referred to as Cohort 1) was designed to detect a meaningful signal of activity while minimizing risk of continuing enrollment under null conditions. Amendment 1 was designed to further explore the optimal regimen by increasing doses of ibrutinib and/or by routine combination with low dose dexamethasone. Cohorts 1 and 3 test activity of ibrutinib monotherapy; Cohorts 2 and 4 test ibrutinib in combination with dexamethasone.

Stage 1:

- Up to eleven (11) subjects were to be enrolled to Cohort 1.
- Up to eighteen (18) subjects will be enrolled to each Cohort 2, 3 and 4.
- Stage 1 enrollment to Cohorts 3 and 4 may begin concurrently after Cohort 2 Stage 1 enrollment is complete. If there is concurrent enrollment, Sponsor will implement centralized assignments into cohorts.

Stage 2:

- If ≥ 2 CBRs are observed among the first 11 subjects in Cohort 1, the cohort will be expanded for up to a total enrollment of 35 subjects.

- If ≥ 3 CBRs are observed within Cohorts 2, 3, or 4 in Stage 1, the cohort(s) may be selected for expansion for up to a total enrollment of 43 subjects in each cohort or until observing ≥ 8 CBRs, whichever occurs earlier.
- If there is concurrent Stage 2 enrollment to more than 1 cohort at any given time, Sponsor will implement centralized assignments into cohorts.

Sponsor maintains the prerogative to select regimen, which gives optimal efficacy and safety results at interim analysis for further development while suspending other cohorts at any time.

The expected total enrollment is between 67 (minimal) and 164 subjects. Dosages and regimens by cohort are summarized in Table 1.

Table 1: Treatment Cohorts and Planned Enrollment

Cohort	Ibrutinib (mg/day)	Dexamethasone	Planned First Stage Enrollment	CBR Criteria for First Stage	Total Enrollment (First and Second Stages)
1	420	Upon progressive disease (PD), 40 mg once weekly is allowed†	11*	≥ 2	35
2	560	40 mg once weekly [#]	18	≥ 3	43
3	840	Upon PD, 40 mg once weekly is allowed†	18	≥ 3	43
4	840	40 mg once weekly [#]	18**	≥ 3	43

* n=11 planned for Cohort 1 First Stage, n=13 were enrolled. The decision for second stage expansion will be based on the number of CBR in the first 11 subjects.

** n=18 planned for Cohort 4 First Stage, n=20 were enrolled. The decision for second stage expansion will be based on the number of CBR in the first 18 subjects.

Dexamethasone administration starts on Cycle 1 Day 4 for Cohort 2 and 4. For Cohort 4 expansion, dexamethasone will be administered starting on Cycle 1 Day 8.

† For Cohorts 1 and 3 subjects who have confirmed PD, and who are clinically stable, without significant worsening of symptoms or hematologic status (ie, meet all entry criteria for the study in regard to symptoms and hematology), will be eligible to receive dexamethasone 40 mg orally once per week in addition to continued treatment with ibrutinib, at the discretion of the investigator.

Subjects are allowed to continue study drug as long as the subject is clinically stable (stable disease [SD] or better) and the subject is not experiencing any unacceptable toxicity. Subjects in the monotherapy cohorts (1 and 3) who have PD confirmed as required by definition in the protocol, and without significant worsening of symptoms or hematologic status (ie, meet all entry criteria for the study in regard to symptoms and hematology), will be eligible to receive dexamethasone 40 mg orally once per week in addition to continued treatment with ibrutinib,

at the discretion of the investigator. Otherwise, subjects having PD will be removed from study. Note that the decision for second stage expansion of Cohorts 1 and 3 will be based on the number of subjects who achieved CBR (MR or better) prior to addition of dexamethasone.

2. STUDY ENDPOINTS

2.1. Primary Endpoint

CBR rate: defined as the proportion of subjects achieving a MR or better as assessed by investigator per the modified IMWG criteria.

2.2. Secondary Endpoints

The secondary endpoints for this study are as follows:

Safety:

- Safety parameters including the incidences and types of clinical adverse events, laboratory variables, and vital signs measurements

Efficacy:

- Duration of clinical benefit (DCB)
- Objective response rate (ORR)
- Duration of objective response (DOR)

Pharmacokinetics:

- Plasma PK of ibrutinib and metabolite PCI-45227

2.3. Exploratory Endpoints

- Progression-free survival (PFS)
- Time to progression (TTP)
- Overall survival (OS)
- Time to Clinical Benefit
- Time to Response

3. SAMPLE SIZE CONSIDERATIONS

Cohort 1 was designed to detect a meaningful signal of activity while minimizing risk of continuing enrollment under null conditions. Cohorts 2-4 were designed to further explore the optimal regimen. The sample size was estimated for each cohort without multiplicity adjustment.

3.1. Cohort 1

Full enrollment to Cohort 1 will be contingent upon Simon 2 stage design rules with a target sample size of 35 evaluable subjects based on meeting interim efficacy endpoints, i.e., if ≥ 2 CBRs are observed among the first 11 subjects within Cohort 1. This study cohort is designed to test the null hypothesis that the CBR rate of ibrutinib monotherapy at a dose of 420 mg/day is $\leq 10\%$ (not clinically compelling) versus the alternative hypothesis that CBR rate will be $\geq 30\%$, at a 1-sided significance level of 5%, with 85% power. Observation of ≥ 7 CBRs within an expanded cohort of 35 subjects will be considered consistent with the alternative hypothesis of CBR rate $\geq 30\%$.

Although the design described above is setup to detect cohort specific CBR rates of 30%, CBR rates as low as 20% is still considered clinically meaningful, as the drug may be developed in combination therapy and/or in less heavily pre-treated populations. With this 2-stage design, the probability to continue enrolling subjects for the second stage is approximately 0.68 if the true CBR rate is 20%.

3.2. Cohorts 2-4

Simon optimal 2-stage study design is utilized in Cohorts 2, 3 and 4.

Up to eighteen subjects will be enrolled to each subsequent cohort (2-4). Stage 1 enrollment to Cohorts 2, 3, and 4 will not be contingent upon results of preceding cohorts. Full enrollment to Cohort 2, 3, and 4 will be contingent upon Simon 2-stage design rules with a sample size of up to 43 evaluable subjects based on meeting interim efficacy endpoints, i.e., if ≥ 3 CBRs are observed among the first 18 subjects within the subject cohort. This design has 80% power to reject the null hypothesis of CBR rate $\leq 10\%$, at a 1-sided significance level of 5%. Observation of ≥ 8 CBRs within an expanded cohort of up to 43 subjects will be considered consistent with the alternative hypothesis of CBR rate $\geq 25\%$. The enrollment of that cohort may be closed early for success once 8 CBRs observed.

Sponsor maintains the prerogative to select regimen that gives optimal efficacy and safety results at interim analysis for further development and suspend other cohorts at any time.

This study design is not powered or intended to allow direct comparison of percent CBR among the cohorts. Results of this study will inform alternative directions for future combination and single agent development in alternative multiple myeloma study populations.

4. STUDY POPULATIONS AND ANALYSIS SETS

The analysis and summary of data for this study will be performed using the following populations:

All enrolled population: All subjects who signed the informed consent form and were enrolled to one of the treatment cohorts. This population will be used to summarize disposition information.

All treated population: All enrolled subjects who received at least one dose of study drug. This population will be used to summarize subject enrollment, demographics, baseline and disease characteristics, prior therapies, and concomitant medications. This population is referred to as the “modified intent-to-treat (mITT) population” in the protocol. This is the primary analysis population for efficacy endpoints.

Response evaluable population: All enrolled subjects who received at least one dose of study drug and underwent at least one response assessment after start of treatment. Response rates (CBR rate and ORR) will be analyzed based on response evaluable population and will be considered as sensitivity analyses.

Safety population: All enrolled subjects who received at least one dose of study drug. This population will be used for analyzing the safety (including dosing) data.

Subjects in treated, response evaluable and safety populations will be analyzed according to the actual treatment received (i.e. as treated).

5. ANALYTIC DEFINITIONS

5.1. Study Day and Duration of Treatment

Study day will be calculated in reference to the date of the first dose of study drug. Study Day 1 corresponds to the date the subject received the first dose of study drug. For assessments/events occurred on or after Study Day 1, study day is calculated as (assessment/event date – date of the first dose of study drug + 1 day). For assessments/events occurred prior to Study Day 1, study day is calculated as (assessment/event date – date of the first dose of study drug). Study Day –1 is the day before Study Day 1. There will not be a Study Day 0.

Treatment duration for ibrutinib will be calculated as the interval from the date of the first dose of ibrutinib to the date of the last dose of ibrutinib. Similarly, treatment duration for dexamethasone will be calculated.

Treatment duration (day) = date of the last dose – date of the first dose + 1 day

5.2. Time on Study

Time on study is defined as the interval between the date of the first dose of study drug and the date last known alive. Subjects who died will be censored at death date.

5.3. Baseline

Unless otherwise specified, the baseline value is defined as the last observation with a non-missing result prior to the start of study drug.

5.4. Disease Status

“Relapsed disease” is defined as the occurrence of progression following a response to a prior therapy. “Refractory” is defined as best response of SD or PD to last line of therapy while on treatment or within 60 days of last therapy.

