## 5.0 SELECTION OF SUBJECTS

### 5.1 Major Inclusion Criteria

#### *Disease Related*

1. Diagnosis of symptomatic MM (as defined by modified IMWG criteria, refer to [Appendix 3](#)) with measurable disease, defined here as having at least one of the following:
  - Serum monoclonal protein (M-protein)  $\geq 0.5$  g/dL as determined by serum protein electrophoresis (SPEP)
  - Urine protein electrophoresis (UPEP)  $\geq 200$  mg/24 hrs
  - Serum free light chain (FLC) assay: involved FLC level  $\geq 10$  mg/dL ( $\geq 100$  mg/L) provided serum FLC ratio is abnormal
2. Relapsed or relapsed and refractory MM after receiving at least 2, but no more than 5, previous lines of therapy, 1 of which must be an immunomodulator (eg, Revlimid®, thalidomide).
  - Refractory myeloma (to most recent treatment) is defined as disease that is nonresponsive while on treatment or progressive disease within 60 days after the completion of preceding treatment. Nonresponsive disease is defined as either failure to achieve minimal response or development of progressive disease while on therapy.
    - Subjects considered refractory to their most recent line of therapy will be ineligible if the most recent line included an immunomodulatory drug and proteasome inhibitor.
  - Relapsed myeloma is defined as the occurrence of any of the following after most recent treatment:
    - $> 25\%$  increase in M-protein from the lowest value obtained while on treatment (absolute increase must be  $\geq 0.5$  g/dL by SPEP,  $\geq 200$  mg/24h by UPEP or  $>10$  mg/dL by serum FLC); or
    - increase in the size and number of lytic bone lesions recognized on radiographs (compression fractures per se do not constitute a relapse).

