### 7.1 Description of Procedures

#### 7.1.1 Screening Assessments

All routine laboratory and clinical screening assessments must be performed within 21 days before the first administration of study drug, unless otherwise indicated (longer windows allowed for baseline radiologic studies). All study-specific assessments that are not part of standard-of-care must be done after subjects sign the ICF.

The following are required:

**Confirmation of Eligibility:** Perform all necessary procedures and evaluations to document that the subject meets each eligibility criterion ([Section 5.0](#)). De-identified copies of measurable disease as documented by SPEP, serum FLC and UPEP is required prior to enrollment.

Multiple myeloma diagnosis will be confirmed as well as the stage at original diagnosis and current disease status (relapsed or relapsed and refractory) will be documented if all requisite clinical results are available. Please refer to the study manual for a more detailed description of the enrollment procedures.

**Medical History:** Collect and record the subject's complete medical history through review of medical records and by interview. Concurrent medical signs and symptoms must be documented to establish baseline severities. A disease history, including the date of initial diagnosis and list of all prior anticancer treatments, and responses and duration of response to these treatments, also will be recorded.

**Concomitant Medications and Therapy:** All concomitant medications and procedures will be collected within 14 days prior to the start of study drug. Prior use of denosumab and bisphosphates should also be recorded.

**Physical Examination, Vital Signs, Height, and Weight:** The screening physical examination (PE) will include, at a minimum, the general appearance of the subject, height (screening only)

and weight, and examination of the skin, eyes, ears, nose, throat, lungs, heart, abdomen, extremities, musculoskeletal system, nervous system, and lymphatic system.

Vital signs (blood pressure, heart rate, respiratory rate, and body temperature) will be assessed after the subject has been resting in the sitting position for at least 3 minutes.

**ECOG Performance Status:** The ECOG index is provided in [Appendix 1](#).

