8.4. Demography and Baseline Disease Characteristics

The following demographic and baseline disease characteristics will be summarized for the all treated population by treatment cohort.

- Demographics: Sex, age (continuous and grouped as <65, ≥65, <70, ≥70, <75, ≥75 years), race, and ethnicity
- Baseline and disease characteristics:
 - Weight and height
 - ECOG performance status (0, 1)
 - Creatinine, estimated creatinine clearance rate (continuous and grouped as < 30, 30-<60, ≥ 60 mL/min)
 - Hematologic abnormalities (hemoglobin [Hgb] < 10 g/dL, platelets < 100×10⁹/L, ANC < 1×10⁹/L)
 - Hemoglobin, platelet counts and ANC
 - Time since initial diagnosis (continuous and grouped as <3, ≥3 years)
 - Disease status (relapsed, relapsed and refractory)
 - Serum β₂-microglobulin (continuous and grouped as <3.5, ≥3.5 - <5.5, ≥5.5 mg/L)
 - Serum albumin (continuous and grouped as <3.5, ≥3.5 g/dL)
 - Disease stage (I, II, III) at baseline per International Staging System (see Table 2)
 - Immunoglobulin heavy chain class (e.g. A, G, M), immunoglobulin light chain class (κ, λ)
 - Measurable disease (SPEP only, UPEP only, SPEP and UPEP, sFLC only)
 - Bone marrow plasma cell percentage
 - Cytogenetic/FISH prognostic markers [e.g. del(17p), del(13q14), t(4;14), t(11;14)]
- Prior cancer-related therapies:
 - Prior radiotherapy (yes, no), prior surgery (yes, no), prior systemic therapy (yes, no)
 - Number of prior systemic therapies (continuous and grouped as 2-3, ≥4)

-
- Type of prior systemic therapies: lenalidomide, thalidomide, pomalidomide, bortezomib, carfilzomib, alkylator (melphalan, cyclophosphamide), doxorubicin, corticosteroid (dexamethasone, prednisone), fludarabine, vincristine, etc.
 - Type of bone marrow or stem cell transplant: autologous, allogeneic
 - Refractory to last line of therapy
 - Refractory to prior immunomodulatory drugs: lenalidomide, thalidomide, pomalidomide
 - Refractory to prior proteasome inhibitors: bortezomib, carfilzomib
 - Refractory to prior immunomodulatory drugs and proteasome inhibitors (i.e. refractory to at least one prior immunomodulatory drug and at least one prior proteasome inhibitor)
 - Last prior treatment [(no PI/IMiD) vs. (PI or IMiD) vs. (PI and IMiD)]
 - Last prior treatment included PI
 - Last prior treatment included IMiD

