8.8.1. Primary Efficacy Endpoint

The primary endpoint of the study is the CBR rate, defined as the proportion of subjects achieving a MR or better prior to initiation of new antineoplastic therapy as assessed by investigator per modified IMWG criteria.

The number and percent of subjects in each best response category (sCR, CR, VGPR, PR, MR, SD, PD) will be summarized by treatment cohort.

CBR rate and its corresponding 2-sided 90% exact binomial confidence interval (CI) will be calculated and presented by treatment cohort. For subjects in Cohorts 1 and 3, CBR will be calculated during ibrutinib monotherapy period (i.e. prior to addition of dexamethasone) as primary analysis. CBR across the whole study course (including ibrutinib and dexamethasone combination therapy period) will be calculated and presented as secondary analysis.

In addition, CBR rate will be analyzed based on response evaluable population and will be considered as sensitivity analyses.

Subgroup Analysis

Subgroup analyses may be performed for the following selected baseline characteristics and potential prognostic variables.

- Sex (male vs. female)
- Age (<65 vs. ≥65 years, <75 vs. ≥75 years)
- Race (Caucasian vs. non-Caucasian)
- Baseline ECOG score (0 vs. 1)
- Baseline hematologic abnormality (yes vs. no); hematologic abnormality: Hgb < 10 g/dL, platelets < $100 \times 10^9/L$ or ANC < $1 \times 10^9/L$
- Disease status (relapsed vs. relapsed and refractory)

-
- Number of prior systemic therapies (2-3 vs. ≥ 4)
 - Refractory status of last line of prior therapy (yes vs. no)
 - Refractory to prior immunomodulatory drugs (yes vs. no)
 - Refractory to prior proteasome inhibitors (yes vs. no)
 - Refractory to prior immunomodulatory drugs and proteasome inhibitors (yes vs. no)
 - FISH abnormalities
 - Del 17p (present vs. absent)
 - t(14;16) (present vs. absent)
 - t(4;14) (present vs. absent)
 - At least a presence of Del 17p, t(14;16) or t(4;14) vs. none of the three
 - Last prior treatment [(no PI/IMiD) vs. (PI or IMiD) vs. (PI and IMiD)]
 - Last prior treatment included PI (yes vs. no)
 - Last prior treatment included IMiD (yes vs. no)

CBR rate and its corresponding 2-sided 90% exact binominal CI will be calculated within each stratum of every subgroup. Forest plot will be provided for the subgroup analyses.

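### SAP 5.4, read literally, classes as not refractory a subject who responded to the last line and then progressed on it or within 60 days; Protocol 5.1 says the opposite

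*SAP*

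**What the plan says.** Protocol 5.1, inclusion criterion 2, defines myeloma refractory to the most recent treatment as "disease that is nonresponsive while on treatment or progressive disease within 60 days after the completion of preceding treatment". It then explains the first term: "Nonresponsive disease is defined as either failure to achieve minimal response or development of progressive disease while on therapy". The synopsis carries the same definition. Together these give three routes to refractory status, and the two that rest on progression do not depend on what response came before.

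SAP 5.4 uses a single phrase: "best response of SD or PD to last line of therapy while on treatment or within 60 days of last therapy". The same section defines relapsed disease as progression after a response to a prior therapy.

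The classification appears in two baseline items in SAP 8.4: disease status (relapsed, or relapsed and refractory) and "Refractory to last line of therapy". Both return as subgroup factors in SAP 8.8.1. Those subgroup analyses are optional for CBR; SAP 8.8.2.2, 8.8.3.1 and 8.8.3.3 state them as planned for ORR, PFS and OS.

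There are two possible sources for the variable. Under Protocol 7.1.1, "current disease status (relapsed or relapsed and refractory) will be documented if all requisite clinical results are available", and the disease history also records a "list of all prior anticancer treatments, and responses and duration of response to these treatments". The SAP does not say which one feeds disease status.

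**The concern.** In the SAP sentence, SD and PD sit side by side after best response, and SAP 8.8.1 lists the same two categories together as best responses on study. A programmer who takes the words at face value would select subjects whose best response to the last line was SD or PD. Anyone with MR or better on that line would be excluded, however soon progression followed.

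The protocol treats such a subject as refractory. The baseline tables could therefore disagree with the definition used at entry and with the status recorded at screening. In single-arm cohorts of relapsed or relapsed and refractory subjects, the refractory share is one of the main descriptors a reader uses to interpret the response rate, so the label should mean the same thing in both documents.

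**Working it through.** No figure in the plan depends on this definition, so there is nothing to reproduce. The check applies three rules to the possible last-line histories.

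- **Rule P (Protocol 5.1):** MR not reached, or PD on therapy, or PD within 60 days after completion.
- **Rule L (SAP 5.4, literal):** best response to the last line is SD or PD. The time phrase can then only mark the period over which response is judged.
- **Rule S (SAP 5.4, second parse):** best response of SD, or else PD on treatment or within 60 days.

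| | Last-line history | P | L | S |
|---|---|---|---|---|
| 1 | MR or better, then PD on therapy | yes | **no** | yes |
| 2 | MR or better, then PD within 60 days after | yes | **no** | yes |
| 3 | MR or better, then PD later than 60 days | no | no | no |
| 4 | SD, then PD on therapy | yes | yes | yes |
| 5 | SD, then PD within 60 days after | yes | yes | yes |
| 6 | SD, PD later than 60 days or none | yes | yes | yes |
| 7 | PD as best response | yes | yes | yes |

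Rule P makes 6 of the 7 histories refractory (all but history 3). Rule L makes 4 refractory (4 to 7), so 6 − 4 = 2 are lost: histories 1 and 2. Rule S makes 6 refractory and loses none.

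These are counts of definitions, not of subjects, and they say nothing about how common each history is. They show two things. First, the loss under Rule L is confined to subjects who responded before progressing. Second, no history is refractory under Rule L but not under Rule P, so any error runs towards too few refractory subjects.

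Histories 1 and 2 meet the SAP's definition of relapsed. Under Rule L they would therefore move from relapsed and refractory to relapsed, and from yes to no on refractoriness to the last line.

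**The case against.** The strongest reply is that the literal reading leaves the time phrase with almost nothing to do. Its two parts, on treatment and within 60 days, mirror the two progression routes in Protocol 5.1. The parse that gives every word a function is the second one, and it matches the protocol exactly. SAP section 1 says changes to the protocol analysis plan are documented in the SAP, and section 10 lists none for this definition. The listing of categories in SAP 8.8.1 concerns on-study response and is weak evidence about prior lines. All of this stands. It makes a faulty paraphrase more likely than a deliberate narrowing, but it does not remove the literal reading.

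Three further points also stand. If disease status is taken from the screening record, that variable is unaffected, leaving the last-line baseline row and its matching split. Protocol 5.1 makes subjects ineligible if they are refractory to a last line that included both an immunomodulatory drug and a proteasome inhibitor, so histories 1 and 2 after such a line should not be in the trial. And the SAP plans no inferential comparison among cohorts.

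It might also be said that the protocol rule needs progression dates that may not have been collected for everyone. This carries less weight. A subject who never reached MR is refractory whatever the timing, so timing matters only for responders, and for them Protocol 7.1.1 has duration of response recorded.

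A reader might infer that the SAP drops progression on therapy altogether. It does not: PD as best response and PD after SD remain refractory under every reading.

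**Conclusion.** The point holds as a minor drafting fault. Applied literally, SAP 5.4 would label as not refractory a subject whom Protocol 5.1 calls refractory, namely one with MR or better on the last line followed by PD on it or within 60 days after it. This would understate the refractory share in the last-line baseline row, in disease status if that is derived under 5.4, and in the two matching descriptive subgroup splits.

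The size in subjects cannot be derived, because the documents give no distribution of last-line histories. The error is zero if the second parse is programmed. For disease status it is also zero if the screening record is used.

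Two stronger inferences are not supported. The documents do not show that the sponsor chose a different definition; section 10 points the other way. Nor is any main result at risk: the primary CBR, its 90% CI, the Simon decisions and the sample size do not use the variable, and eligibility follows the protocol text.

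**What to change.** Replace the refractory sentence in SAP 5.4 with the three Protocol 5.1 routes (failure to achieve MR, or PD while on therapy, or PD within 60 days after completing the most recent treatment), or cross-refer to Protocol 5.1. It would help to state in the same place whether disease status is derived from prior-therapy data or taken from the screening record, but that is added detail and not the correction itself.

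The cost is one SAP sentence. The treatment and response history that Protocol 7.1.1 already collects should be enough to apply the rule, although the case report forms are not in the documents to confirm this. No analysis method changes. If a best-response definition was in fact intended, it belongs in SAP section 10 as a stated departure from the protocol.
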